All subjects who finish BL assessments and meet inclusion/exclusion criteria will be randomized into one of two groups, "Active eTMS" and "Sham eTMS", in a 1:1 ratio, stratified by clinic. Stage 2 will consist of a randomized period and an open-label period. During the randomized period, the Active eTMS group will receive Active eTMS and the Sham eTMS group will receive Sham eTMS twice per day, with 20 total treatments delivered in a 2 or 3-week period. Following the randomized period of the study, all Sham eTMS subjects will have the option of participating in the open-label portion of the study. Those who choose to participate in open-label treatment will receive 20 Active eTMS sessions, twice per day, which must be completed in a period of 21 calendar days.

All groups will undergo an assessment of symptoms at baseline, before Week 6 (F1), and then again at the end of Week 10 (F2). The primary efficacy endpoint, and outcome time point, is Wave Neuroscience, Inc. Protocol eTMS-PTSD Rev 1.1 11 January 2024 PAGE 28 change in Post-Traumatic Stress Disorder symptoms between the Baseline (BL) and the first follow-up (F1). The primary efficacy outcome will be measured using the PCL-5. Safety outcomes will be measured by recording adverse events, incidence and type.

PARTICIPANT POPULATION

The enrollment goal for the combined two stages of the study is 170 participants of any gender or ethnic background, age 22-65 years, with Post-Traumatic Stress Disorder. Thirty (30) participants will be part of Stage 1 and be provided with open-label treatment to evaluate safety of eTMS in this population. 140 participants will be part of Stage 2, randomized to either active or sham eTMS, in a 1:1 allocation ratio, stratified by recruitment site. Participants randomized to sham eTMS in Stage 2 will receive an additional series of open-label active eTMS following the randomized portion of Stage 2.

Inclusion Criteria

Participants must meet all following inclusion criteria to qualify for enrollment into the study:

- 1. Willing and able to consent to participate in the study via signed Informed Consent
- 2. Age 22 65 years
- 3. Provisional diagnosis of PTSD according to Veterans Administration PCL-5 rubric fulfillment AND cutpoint score of 31 or above
- 4. Positive identification as either a Veteran, or First Responder (e.g., emergency medical service provider, firefighter, or any other emergency response personnel)

Exclusion Criteria

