In the randomized, blinded, Stage 2 of the trial, post-trial access to the active study treatment will be provided. For both ethical and recruitment purposes, there will be up to 20 additional treatments of open-label active eTMS treatment offered to participants who are part of the Sham eTMS Group who complete 75% of their assigned blinded treatment (15 treatments), unless the site PI in consultation with the Medical Monitor deem active treatment not to be in the best interests of the participant or of the study personnel (e.g., if the participant begins medications that lower seizure threshold, or experiences an adverse event such as a negative health or psychological event that would have excluded them from the blinded study).

Basis of Study Treatment Parameter Selection

Treatment with rTMS (repetitive transcranial magnetic stimulation) requires the specification of many treatment parameters. Within-session parameters that must be specified include stimulus waveform (square wave, triangle wave, sine wave), coil geometry (depth-focality tradeoff), field intensity, frequency of stimulation during the pulse train, duration of the pulse train, duration of the quiet period, number of pulse train-quiet period cycles in the treatment session. Course-of-treatment parameters that must be specified include the number of treatment sessions and the spacing of sessions.

As is the case with many forms of medical treatment, understanding of the mechanism of rTMS action is incomplete. A review by Leuchter, et al. (Leuchter, Cook, Jin, & Phillips, 2013) considered the mechanism of action in rTMS treatment of depression. The authors concluded that benefits of rTMS were tied to enhanced neuroplasticity and the resetting of corticothalamic pathways. While this assessment may provide a conceptual basis for an understanding, it does not provide quantitative specification of treatment parameters. This being the case, our best recourse was to review the prior clinical literature.

The greatest body of prior experience is in the treatment of depression. Most rTMS treatments for depression were carried out with standardized stimulation parameters, typically left dorsolateral prefrontal cortex using 10 Hz stimulation at 120% of motor threshold. The early cleared rTMS devices used this standard 10 Hz protocol – largely 37.5-minute sessions, 5 days

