PHQ-SADS, AUDIT, DAST-10, OCS, PSQI		х			x
CSSRS		Х			Х
Concomitant Treatments, Medications, Illicit Drug and Alcohol use		х	х	x	х
SEQ/AEs		Х	х	Х	Х
EEG		х			Х
МТ			Х		
eTMS			Х	Х	

TABLE 4: STAGE 1 SCHEDULE OF ACTIVITIES

Notes:

- 1. All eTMS treatments in Stage 1 are open-label active stimulation
- 2. Safety stage (Stage 1) study days are labeled SD to differentiate them from randomized stage (Stage 2) study days, labeled RD and from the open-label (Stage 2) days, labeled OD

TABLE 5: STAGE 2 SCHEDULE OF ACTIVITIES

	Enrol	llment		Study Treatment in Clinic	Follow-Up (F) Evaluations				
Procedures	sc	BL	Day 1	Days 2 through 35	(F1)	(F2)	(F3)		
Acceptable windows	RD-28 to RD-2	RD-28 to RD-1	RD+1	RD+2 to RD+21	RD+10 to RD+21	RD+71 to RD+77	RD+176 to RD+196		
Phone Screen	Х								
Informed Consent	Х								
MMSE, TMSs		Х							
Demographics		Х							
DHQ, BPI		Х			Х				
LEC-5, OSU-TBI-ID		Х							
Medical History/Physical, CGI		Х			Х	х	х		
Braincheck		Х	Х		Х				
VR-36, PCL-5		Х			Х	Х	Х		
PHQ-SADS, AUDIT, DAST-10, OCS, PSQI		х			Х				
CSSRS		Х			Х	х	Х		
Concomitant Treatments, Medications, Illicit Drug and Alcohol Use		x	х	x	х	x	x		
SEQ/AEs		Х	Х	Х	Х	х	X		
EEG		Х			Х				
MT			Х						
eTMS: (Active/Sham)			Х	Х					

Notes:

1. The F1 EEG may serve as the treatment-setting EEG for Open Label if conducted within 15 days of beginning OL treatment

TABLE 6: STAGE 2 OPEN-LABEL SCHEDULE OF ACTIVITIES

	Open-label eligibility	Open-Label Active eTMS in Clinic				
Procedures	EL	Day 1	Days 2 through 21			
Acceptable windows	Within 60 days of F1 completion	OD+1	OD+2 to OD+21			
Open Label Eligibility Review	Х					
Concomitant Treatments and Medications, MED, OCS		Х	Х			
SEQ/AEs		Х	Х			
EEG	X ³					
МТ		Х				
eTMS		Х	Х			

Notes:

- 1. All Stage 2 Sham-assigned participants who complete 75% of assigned study treatments during the randomized period may opt-in for up to 20 open label active eTMS treatments. They must continue to be safe to receive eTMS treatment as determined from data collected at the F1 data collection visit and prior to the first open label treatment.
- 2. The eligibility determination for open-label treatment (reviewed and signed by the Investigator) shall be made within 60 days of the completion of the F1 data collection in the randomized period.

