Poolability over study sites will be separately assessed. In a separate analysis the association between the primary endpoint and the study site will be explored. Both the main effect of study site and the interaction between study site and treatment group will be explored.

Additional Analyses of the Primary Outcome

Exploratory responder analyses will be conducted. To determine whether a greater percentage of Active-treated participants respond to study treatment than Sham-treated participants, the binomial z-test will be used to compare the Active-treated group to the Sham-treated group at a number of percentage reductions in PCL-5 scores as candidate values of a successful treatment response. A range of percentage reduction values will be investigated as possible discriminating values to assist in designing future trials regarding sample size justification and power analysis, should a trial in future be designed with a responder analysis as the primary outcome or a secondary outcome.

Other participant reported outcomes analyses

Other participant reported outcomes, including assessment of blinding, will be analyzed according to their level of data (e.g., quantitative, rank order, or categorical) and validity of statistical assumptions required (e.g., homoscedasticity and normality).

Electrophysiological data analyses

Quantitative EEG data collected at BL and F1 will be stored on hard disk and analyzed offline. Raw data of each record will be visually inspected to reject significant artifact contamination. Selective data will be further analyzed by fast Fourier transform (FFT) routine to yield four consecutive frequency bands – delta (0.5-4 Hz), theta (4-8 Hz), alpha (8-13 Hz) and beta (13-35 Hz). Power density of each frequency band of each channel will be used to measure the EEG changes after treatment. Statistical analysis will include data reduction by initial factor analysis. Difference between treatment groups at each recording time will be tested by repeated measures and regression of number of treatments by channel. It is anticipated that successful treatment will result in reductions in low frequency rhythms and increases in peak alpha frequency and correspondent narrow-band density. These changes in EEG variables will be further correlated with clinical and cognitive data to explore the hypothesis that EEG parameters could be a biomarker for PTSD.

STUDY SITE MONITORING

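### The exploratory EEG analysis names session count as a test of the arm difference, but session count is planned to be equal in both arms, and no arm or baseline term is stated

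*Combined protocol and SAP*

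**What the plan says.** The section on electrophysiological data analyses sets out the EEG work in one paragraph. On timing: "Quantitative EEG data collected at BL and F1 will be stored on hard disk and analyzed offline". On the quantity of interest: "Power density of each frequency band of each channel will be used to measure the EEG changes after treatment". On the comparison of arms: "Difference between treatment groups at each recording time will be tested by repeated measures and regression of number of treatments by channel". The resulting changes are then correlated with clinical and cognitive data to "explore the hypothesis that EEG parameters could be a biomarker for PTSD".

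On session count, the Stage 2 part of the Study Design section says that "the Active eTMS group will receive Active eTMS and the Sham eTMS group will receive Sham eTMS twice per day, with 20 total treatments". Sham sessions are themselves called treatments. Note 1 to Table 6 speaks of "All Stage 2 Sham-assigned participants who complete 75% of assigned study treatments during the randomized period", and the Open Label Treatment section equates 75% of the sham course with 15 treatments.

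The primary outcome section is more explicit. The PCL-5 model names baseline score and a treatment-group dummy as its regressors. The list of candidate imputation covariates shows the group dummy and the number of treatments as separate variables.

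**The concern.** The comparison announced is between arms, yet one of the two named tools is a regression on a variable that does not define the arms. By design the session count is 20 on each side, so whatever variation it has comes from who missed sessions.

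That variation arises after randomisation. The investigator may suspend treatment while data collection continues (Withdrawal from Study), and sessions not done within 21 calendar days are not made up (Study Treatment Parameters). Attendance can therefore follow the participant's state, and a slope on it is not protected by randomisation.

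The other tool, repeated measures, is named without saying which effect is the test. Taken at its word, testing at each recording time includes a test at BL. There the arms differ only by chance, so that test says nothing about eTMS. At F1 the text does not say whether the participant's own BL recording enters the model.

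At stake is how far the EEG findings can be trusted. If the model is left open across channels and bands, it can be settled after the data are seen, and these EEG changes feed the biomarker correlations.

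**Working it through.** **Inputs from the documents.** Two EEG recordings are analysed, BL and F1. Both arms have 20 scheduled sessions. There are 54 completers per group, two-sided alpha is 0.05, and allocation is 1:1. The sample-size section gives these last figures for the PCL-5. (The Study Design section gives 140 randomised and 126 completers instead, which is a separate inconsistency; I use 54 per arm.)

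**The plan's own figure.** The documents give no EEG power, effect size or SD. The PCL-5 power does reproduce: 15 / (18.68 × √(2/54)) = 4.17, and a noncentral t on 106 df gives 0.9852 against the stated .985. Nothing below depends on it.

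**Assumptions, because the documents are silent.** A true arm effect of 0.5 SD at F1 or none, a BL-F1 EEG correlation ρ over a range, and the attendance patterns stated below.

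**Step 1: session count alone, true arm effect present.** Simulation, 4,000 runs, ρ = 0.5 and 0.7. Half of the participants were liable to miss a few of the 20 sessions, with the same pattern in both arms. The effect was either constant at 0.5 SD or proportional to active sessions received (0.5 SD at 20). A regression of F1, or of change, on session count alone rejected in 4.8% to 5.8% of runs. The arm term in a model with arm, sessions, their interaction and BL had power 0.81 to 0.95.

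**Step 2: session count alone, no arm effect.** Simulation, 4,000 runs per setting. Here 30% of participants miss 1 to 10 sessions, selected by a latent variable correlated 0.3 with BL EEG.

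| ρ | F1 on sessions | change on sessions | F1 on sessions and BL |
|---|---|---|---|
| 0.3 | 9% | 22% | 5% |
| 0.6 | 22% | 15% | 5% |
| 0.8 | 36% | 10% | 5% |

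Arm comparisons stayed at about 5% throughout. The excess disappears when BL EEG is in the model, because in this set-up attendance is linked to EEG only through BL.

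**Step 3: precision of the arm contrast.** Relative to an F1-only comparison, the variance is 2(1 − ρ) for arm-by-time (the difference in change) and 1 − ρ² for F1 adjusted for BL. So, against BL-adjusted F1, the variance is 1/(1 − ρ²) times larger for F1-only and 2(1 − ρ)/(1 − ρ²) = 2/(1 + ρ) times larger for arm-by-time. Power is Φ(0.5/(k√(2/54)) − 1.960), with k = 1, √(2(1 − ρ)) or √(1 − ρ²). For F1-only this is Φ(2.598 − 1.960) = 0.738.

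| ρ | power, F1-only | power, arm-by-time | power, BL-adjusted F1 | variance ratio, F1-only | variance ratio, arm-by-time |
|---|---|---|---|---|---|
| 0.3 | 0.738 | 0.593 | 0.777 | 1.10 | 1.54 |
| 0.5 | 0.738 | 0.738 | 0.851 | 1.33 | 1.33 |
| 0.7 | 0.738 | 0.918 | 0.953 | 1.96 | 1.18 |

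BL-adjusted F1 has the highest power in each row.

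**The case against.** A reader might infer that the plan ignores baseline EEG. The documents do not support that. Repeated measures is named, BL is one of only two recordings, and the paragraph speaks of change after treatment. If an arm-by-time test is meant, BL is already used, and at high ρ little is lost against the adjusted model. This objection stands, so the precision loss is conditional. A reading in which the test is an arm effect averaged over BL and F1 is also strained, since the text says at each recording time.

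A reader might infer that arm is left out of the session regression. The text does not say so. It is silent on terms, and the sentence offers the regression as a way to test a group difference, so a comparison of session-response slopes between arms would fit. The synopsis also says that sham participants receive no treatment. If sham were coded as zero sessions, the regressor would be largely an arm indicator blurred by attendance. Neither version is written down, and elsewhere the plan counts sham sessions as treatments and lists arm and session count as different variables.

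A reader might also infer that a session-count result will be presented as an arm effect. Nothing in the documents says how it would be reported.

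The false-rejection figures rest on an assumed link between attendance and EEG, for which the documents give no evidence. They also change with the outcome and vanish with BL in the model. Finally, EEG is exploratory: no alpha, sample size or stopping decision depends on it.

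**Conclusion.** The concern holds in a limited form. As literally written, with no arm or arm-by-sessions term stated, a regression on number of treatments does not test a difference between arms. It rejects at about its nominal 5% under an assumed 0.5 SD arm effect with 54 per arm. It can also reject with no arm effect if attendance is related to EEG: about 9% to 36% at an assumed correlation of 0.3, depending on ρ and on whether F1 or change is the outcome. The BL arm test is uninformative under randomisation.

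Whether precision is lost depends on what repeated measures means. The cost against BL-adjusted F1 is a variance 1/(1 − ρ²) times larger for F1-only, or 2/(1 + ρ) times larger for arm-by-time, and the documents give no EEG ρ. The primary PCL-5 analysis already carries baseline and arm terms, and its conclusion is unaffected. The change is worth making because it replaces an unclear method with one at least as powerful at every correlation checked, using recordings that the trial already collects.

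**What to change.** Replace the sentence on testing group differences with wording such as: for each EEG measure or factor score, the F1 value will be regressed on treatment group and the BL value of the same measure, among randomised participants with usable recordings at both times; the treatment-group coefficient is the test of the arm difference.

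Drop the comparison of arms at BL. Keep number of treatments only as a descriptive relation within the active arm, labelled as non-randomised. The planned factor-analytic reduction can stay, since the same model applies to factor scores.

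The cost is SAP wording only, with no new data or visits. The session-count result becomes descriptive, and participants without a usable recording at BL or F1 do not contribute, which the report should state with counts by arm.
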